12.1.5 Suspected transmission of an infectious agent via a medicinal product

For the purposes of reporting, any suspected transmission of an infectious agent via a medicinal product should be considered as an SAE; such cases must be reported immediately, recorded in the AE module of the eCRF, and followed as any other SAE. Any organism, virus, or infectious particle (eg, prion protein transmitting transmissible spongiform encephalopathy), pathogenic or nonpathogenic, is considered an infectious agent.

12.1.6 Overdose of investigational medicinal product

Excessive dosing (beyond that prescribed in the protocol and including overdose) should be recorded in the eCRF. Any SAE or nonserious AE associated with excessive dosing must be followed as any other SAE or nonserious AE. These events are only considered AEs or SAEs if there are associated clinical signs and symptoms or if the act of taking the excess medicine itself is an AE or SAE (eg, suicide attempt).

12.1.7 Safety signal detection

Selected data from this study will be reviewed periodically to detect as early as possible any safety concern(s) related to the IMP so that Investigators, clinical study subjects, regulatory authorities, and IRBs/IECs will be informed appropriately and as early as possible.

In addition, an independent Data Monitoring Committee (DMC) will periodically review and monitor safety data from this study and advise UCB. Details are provided in the DMC Charter.

Cardiovascular and Neuropsychiatric Adjudication Committees will also periodically review and monitor safety data from this study and advise UCB. Details are provided in the Adjudication Committee Charters.

The Study Physician or medically qualified designee/equivalent will conduct an ongoing review of SAEs and perform ongoing SAE reconciliations in collaboration with the PS representative.

As appropriate for the stage of development and accumulated experience with the IMP, medically qualified personnel at UCB may identify additional safety measures (eg, AEs, vital signs, laboratory or ECG results) for which data will be periodically reviewed during the course of the study.

12.2 Laboratory measurements

Clinical laboratory assessments consist of serum chemistry, hematology, urinalysis, and urine drug screen. A centralized laboratory will be used to supply all laboratory test supplies and analyze all blood and urine samples for hematology, biochemistry, and urinalysis measurements. Any unscheduled laboratory testing should also be collected using the central laboratory. Testing to rule out hepatitis B, hepatitis C, and HIV (see Exclusion Criterion #9, Section 6.2) will be performed at Screening in addition to those measurements listed in Table 12–2.

Specific details regarding the handling and processing of serum chemistry, hematology, and urinalysis samples are provided in the study laboratory manuals.

The following laboratory parameters will be measured:

Table 12–2: Laboratory measurements

Hematology	Chemistry	Urinalysis dipstick ^a
Basophils	Calcium	pH
Eosinophils	Chloride	Albumin (protein)
Lymphocytes	Magnesium	Glucose
Monocytes	Potassium	Blood
Neutrophils	Sodium	Leukocyte esterase
Hematocrit	Glucose	Nitrite
Hemoglobin	BUN	Urine dipstick for pregnancy testing ^b
MCH	Creatinine	Urine drug screen ^c
MCHC	ALP	
MCV	AST	
Platelet count	ALT	
RBC count	GGT	
WBC count	Total bilirubin	
	Serum pregnancy testing ^a	

ALP=alkaline phosphatase; ALT=alanine aminotransferase; AST=aspartate aminotransferase; BUN=blood urea nitrogen; GGT=gamma-glutamyltransferase; MCH=mean corpuscular hemoglobin; MCHC=mean corpuscular hemoglobin concentration; MCV=mean corpuscular volume; PEOT=Premature End of Treatment; RBC=red blood cell; SFU=Safety Follow-Up; WBC=white blood cell

- ^a A urine microscopic examination will be performed if the result for albumin (protein), leukocyte esterase, blood, or nitrite is abnormal. A urine microscopic examination will include: WBC, RBC, epithelial cells (squamous, transitional, and renal tubular), hyaline casts, WBC casts, RBC casts, waxy casts, granular casts, calcium oxalate crystals, uric acid crystals, triphosphate crystals, yeast, bacteria, amorphous urates, and amorphous phosphates.
- ^b Pregnancy testing will consist of serum testing at the Screening Visit. The pregnancy test will be urine at all other visits.
- ^c Urine drug screen will be performed at Screening Visit, and Week 56 or PEOT Visit.

12.2.1 Evaluation of PDILI

The PDILI IMP discontinuation criteria for this study are provided in [Section 6.3.1](#), with the accompanying required follow-up investigation and monitoring detailed below. All PDILI events must be reported as an AE and reported to the study site and Sponsor within 24 hours of learning of their occurrence. Any PDILI event that meets the criterion for potential Hy's Law must be reported as an AESI (see [Section 12.1.1.3](#)), and, if applicable, also reported as an SAE (see [Section 12.1.1.2](#)).

Evaluation of PDILI consists of the diagnostic testing and continued monitoring included in [Table 12–3](#) (specific tests dependent on laboratory results and corresponding symptoms) and consultation with a local hepatologist (if applicable; discussed in [Section 12.2.1.1](#)). The local hepatologist is the expert usually consulted by the treating physician for assessment and management of potential hepatic disease. This would usually be a hepatologist, but may be a gastroenterologist. Additional investigation and monitoring may be required and adapted based on the diagnosis after the cause of the liver injury/abnormality is confirmed (details in [Section 12.2.1.4](#)).

The results of all monitoring, including laboratory testing and other testing, should be made available to the study site and Sponsor.

All initial tests resulting in abnormal hepatic laboratory values need to be repeated, but appropriate medical action must not be delayed waiting for the repeat result.

If tests are done locally for more rapid results, a concurrent sample should also be sent to the central laboratory whenever possible. Medical care decisions are to be made initially using the most rapidly available results and a conservative approach must be taken if the results from the 2 laboratory tests are significantly different. Data from the local and central laboratory are to be recorded on the applicable eCRF pages.

When IMP is discontinued, all concomitant medications and herbal supplements that are not medically necessary should also be discontinued. In these cases, the Investigator should also consider dose reduction for medically necessary concomitant medication and consider changing any medically required concomitant medication known to be hepatotoxic to a suitable alternative.

When IMP is stopped due to PDILI (as described in [Section 6.3.1](#)), IMP must be permanently discontinued unless a subsequent alternative diagnosis fully explains the hepatic findings. If a subsequent alternative diagnosis fully explains the hepatic findings, and the requirements provided in [Section 12.2.1.2.1](#) are met, rechallenge with IMP may be appropriate.

[Table 12–3](#) summarizes the approach to investigate PDILI.

Table 12–3: Required investigations and follow-up for PDILI

Laboratory value			Immediate		Follow up	
ALT or AST	Total bilirubin	Symptoms ^a of hepatitis or hypersensitivity	Consultation requirements	Actions	Testing	Evaluation
≥3xULN	≥2xULN ^b	NA	Hepatology consult ^c Medical Monitor must be notified within 24 hours (eg, by laboratory alert) and subject discussed with Medical Monitor ASAP.	Immediate, permanent IMP discontinuation.	Essential: Must have repeat liver chemistry values and additional testing completed ASAP (see Section 12.2.1.3); recommended to occur at the site with HCP.	Monitoring of liver chemistry values at least twice per week until values normalize, stabilize, or return to within baseline values. ^d
≥3xULN	NA	Yes				
≥8xULN	NA	NA	Need for hepatology consult to be discussed (required if ALT or AST ≥8xULN). Medical Monitor must be notified within 24 hours (eg, by laboratory alert) and subject discussed with Medical Monitor ASAP.	Immediate, permanent IMP discontinuation.		

Table 12–3: Required investigations and follow-up for PDILI

Laboratory value			Immediate		Follow up	
ALT or AST	Total bilirubin	Symptoms ^a of hepatitis of hypersensitivity	Consultation requirements	Actions	Testing	Evaluation
≥5xULN (and ≥2x baseline) and <8xULN	<2xULN	No	
Discussion with Medical Monitor required.
 
Consider need for hepatology consult if there is no evidence of resolution (see Follow up requirements).^c
	
Further investigation – immediate IMP discontinuation not required (see Section 12.2.1.2).
 
IMP discontinuation required if any of the following occur:
 
 • Subject cannot comply with monitoring schedule. • Liver chemistry values continue to increase. • Liver chemistry values remain ≥5xULN (and ≥2x baseline) after 4 weeks of monitoring without evidence of resolution. 	
Essential: Every attempt must be made to have repeat liver chemistry values and additional testing completed within 48 hours at the site with HCP (see Section 12.2.1.3).
	
Monitoring of liver chemistry values at least twice per week for 2 weeks.^d
 
 • Immediate IMP discontinuation required if liver chemistry values continue to increase. 
After 2 weeks of monitoring liver chemistry values:
 
 • ALT or AST remains ≥5xULN <8xULN, IMP should be temporarily withheld and subject should undergo repeat test in 2 weeks. 
Continue IMP if ALT or AST values <5xULN; continue to monitor at least twice per week until values normalize, stabilize,

Table 12–3: Required investigations and follow-up for PDILI

Laboratory value			Immediate		Follow up	
ALT or AST	Total bilirubin	Symptoms ^a of hepatitis of hypersensitivity	Consultation requirements	Actions	Testing	Evaluation
						
or return to within baseline values.
 
If ALT or AST remains $\geq 5 \times \text{ULN}$ after second re-test, immediate, permanent IMP discontinuation required.
 
Continue to monitor until values normalize, stabilize, or return to within baseline values.^d

ALP=alkaline phosphatase; ALT=alanine aminotransferase; ASAP=as soon as possible; AST=aspartate aminotransferase; HCP=healthcare practitioner;

IMP=investigational medicinal product; NA=not applicable; PDILI=potential drug-induced liver injury; ULN=upper limit of normal

^a Hepatitis symptoms include fatigue, nausea, vomiting, and right upper quadrant pain or tenderness; hypersensitivity symptoms include eosinophilia (>5%), rash, and fever (without clear alternative cause).

^b If the subject also has $\geq 2 \times \text{ULN}$ ALP, the possibility of an indication of biliary obstruction should be discussed with the Medical Monitor.

^c Details provided in [Section 12.2.1.1](#). The local hepatologist is the expert usually consulted by the treating physician for assessment and management of potential hepatic disease. This would usually be a hepatologist, but may be a gastroenterologist.

^d Unless an alternative monitoring schedule is agreed by the Investigator and UCB responsible physician. Determination of stabilization is at the discretion of the Investigator in consultation with the hepatologist (as applicable) and UCB responsible physician, as needed.

12.2.1.1 Consultation with Medical Monitor and local hepatologist

Potential drug-induced liver injury events require notification of the Medical Monitor within 24 hours (eg, by laboratory alert), and the subject must be discussed with the Medical Monitor as soon as possible. If required, the subject must also be discussed with the local hepatologist. The local hepatologist is the expert usually consulted by the treating physician for assessment and management of potential hepatic disease. This would usually be a hepatologist, but may be a gastroenterologist. If determined necessary, this discussion should be followed by a full hepatology assessment (see [Section 12.2.1.3](#)) and SAE report (if applicable).

12.2.1.2 Immediate action: determination of IMP discontinuation

All PDILI events require immediate action, testing, and monitoring.

The immediate action is dependent on the laboratory values and symptoms of hepatitis or hypersensitivity and ranges from continuation of IMP (followed by immediate investigation) to immediate and permanent discontinuation (see [Section 6.3.1](#) and [Table 12-3](#) for details).

When IMP is discontinued, all concomitant medications and herbal supplements that are not medically necessary should also be discontinued. The Investigator should also consider dose reduction for medically necessary concomitant medication and consider changing any medically required concomitant medication known to be hepatotoxic to a suitable alternative.

12.2.1.2.1 IMP restart/rechallenge

Rechallenge with IMP can occur only if ALL of the following requirements are met:

- The results of additional testing and monitoring described in [Section 12.2.1.3](#) and [Section 12.2.1.4](#) confirm a nondrug-related cause for the abnormal hepatic laboratory parameters and any associated symptoms (ie, a subsequent alternative diagnosis fully explains the hepatic findings).
- The subject has shown clear therapeutic benefit from the IMP.
- Subject's ALT or AST elevations do not exceed $\geq 5xULN$.
- Subject's total bilirubin is $< 2xULN$.
- Subject has no signs or symptoms of hypersensitivity or hepatitis.
- The rechallenge is approved by the UCB responsible physician, DMC, and a hepatologist. The hepatologist must be external to UCB but may be a member of the DMC. It is recommended that the hepatologist be a local hepatology expert or the hepatologist treating the subject.
- Subject agrees to the Investigator-recommended monitoring plan.

12.2.1.3 Testing: identification/exclusion of alternative etiology

The measurements and additional information required for the assessment of PDILI events when there is a reasonable possibility that they may have been caused by the IMP are detailed in [Table 12-4](#) (laboratory measurements) and [Table 12-5](#) (additional information). Results of the laboratory measurements and information collected are to be submitted to the Sponsor on the corresponding eCRF. If the medical history of the subject indicates a requirement for other

assessments not included below, these additional assessments should be completed and submitted, as applicable.

All blood samples should be stored, if possible. If tests are done locally for more rapid results, a concurrent sample must also be sent to the central laboratory.

The following measurements are to be assessed:

Table 12–4: PDILI laboratory measurements

Virology-related	Hepatitis A IgM antibody
	HBsAg
	Hepatitis E IgM antibody
	HBcAb-IgM
	Hepatitis C RNA
	Cytomegalovirus IgM antibody
	Epstein-Barr viral capsid antigen IgM antibody (if unavailable, obtain heterophile antibody or monospot testing)
Immunology	Anti-nuclear antibody (qualitative and quantitative)
	Anti-smooth muscle antibody (qualitative and quantitative)
	Type 1 anti-liver kidney microsomal antibodies (qualitative and quantitative)
Hematology	Eosinophil count
Urinalysis	Urine drug screen ^a
Chemistry	Amylase
	Sodium, potassium, chloride, glucose, BUN, creatinine
	Total bilirubin, ALP, AST, ALT, GGT, total cholesterol, albumin
	If total bilirubin $\geq 1.5 \times \text{ULN}$, obtain fractionated bilirubin to obtain % direct bilirubin
	Serum CPK and LDH to evaluate possible muscle injury causing transaminase elevation
Additional	Prothrombin time/INR ^b
	Serum pregnancy test ^c
	PK

ALP=alkaline phosphatase; ALT=alanine aminotransferase; AST=aspartate aminotransferase; BUN=blood urea nitrogen; CPK=creatine phosphokinase; GGT=gamma glutamyl transferase; HBcAb-IgM=hepatitis B core antibody-IgM; HBsAg=hepatitis B surface antigen; IgM=immunoglobulin M; INR=international normalized ratio; LDH=lactate dehydrogenase; PDILI=potential drug-induced liver injury; PK=pharmacokinetic; RNA=ribonucleic acid; ULN=upper limit of normal

Table 12–4: PDILI laboratory measurements

- ^a Tests in addition to the specified analytes may be performed based on the Investigator’s medical judgment and subject history.
- ^b Measured only for subjects with ALT >8xULN, elevations in total bilirubin, and symptoms of hepatitis or hypersensitivity. Hepatitis symptoms include fatigue, nausea, vomiting, and right upper quadrant pain or tenderness; hypersensitivity symptoms include eosinophilia (>5%), rash, and fever (without clear alternative cause).
- ^c For women of childbearing potential.

The following additional information is to be collected:

Table 12–5: PDILI information to be collected

New or updated information
Concomitant prescription and over-the-counter medications (eg, acetaminophen, herbal remedies, vitamins); dosages and dates should be included.
Pertinent medical history, including the following: 
 • History of liver disease (eg, autoimmune hepatitis, nonalcoholic steatohepatitis or other “fatty liver disease”) • Adverse reactions to drugs • Allergies • Relevant family history or inheritable disorders (eg, Gilbert’s syndrome, alpha-1 antitrypsin deficiency) • Recent travel
Progression of malignancy involving the liver (Note: Metastatic disease to the liver, by itself, should not be used as an explanation for significant AST and/or ALT elevations.)
The appearance or worsening of clinical symptoms of hepatitis or hypersensitivity (eg, fatigue, nausea, vomiting, right upper quadrant pain or tenderness, decreased appetite, abdominal pain, jaundice, fever, or rash)
Recent clinically significant hypotension or hypoxemia with compromised cardiopulmonary function
Alcohol and illicit drug use
Results of liver imaging or liver biopsy, if done
Results of any specialist or hepatology consult, if done
Any postmortem/pathology reports

ALT=alanine aminotransferase; AST=aspartate aminotransferase; PDILI=potential drug-induced liver injury

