4.3.3 Pharmacokinetic variable

The PK variable is the plasma concentration of bimekizumab.

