7.9 Blinding

Due to differences in presentation between the bimekizumab and adalimumab, special precautions will be taken to ensure study blinding and study sites will have blinded and unblinded personnel.

All Sponsor and Investigator site personnel involved in the study will be blinded to the randomized IMP assignment with the following exceptions:

- Unblinded study staff will be responsible for preparation (breaking tamper proof sticker on kit, etc) of the clinical trial material, including recording the administration information on source documents, and administration of the IMP as sc injections. The unblinded personnel will not be involved in the study in any way other than assuring the medication is taken from the correct kit and administering the drug to the subjects.
- Bioanalytical staff analyzing blood samples for bimekizumab and anti-bimekizumab antibody determination.

During the study, the Sponsor will provide blinded and unblinded site monitors for the purposes of verifying safety, efficacy, and drug administration and documentation records. Unblinded study site personnel need to be available in order to resolve queries. Study monitors and study site personnel blinded to treatment assignment will not discuss or have access to any drug-related information.

Study sites will be required to have a written blinding plan in place, signed by the Principal Investigator, which will detail the site's steps for ensuring that the double-blind nature of the study is maintained. Sites will be instructed to keep study subjects blind to the IMP as detailed in the site blinding plan.

Further details are provided in the study manual and site blinding plan.

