10 ASSESSMENT OF PHARMACOKINETIC AND PHARMACOGENOMIC VARIABLE(S)

10.1 Pharmacokinetic variables

Blood samples for measurement of PK assessments ([Section 4.3.3](#)) will be collected at the time points specified in the schedule of study assessments ([Table 5–1](#)).

At dosing visits, blood samples will be drawn prior to dosing, and will be drawn at the same time of the sampling for clinical laboratory tests. The time and date of collection will be recorded in the eCRF.

Instructions pertaining to sample collection, processing, storage, labeling, and shipping are provided in the laboratory manual for this study. Detailed information on sample analysis will be provided in a bioanalytical report.

Pharmacokinetic samples from subjects receiving adalimumab will not be analyzed, but stored for potential future PK analysis and anti-drug antibody determination.

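### The liver-injury work-up routes a PK result to the Sponsor and site without exemption, contradicting the blinding section; before Week 24 a returned concentration would identify a bimekizumab arm

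*Protocol*

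**What the plan says.** Protocol 12.2.1.3 sets out the tests for PDILI events in which the IMP may plausibly be the cause. Table 12-4 lists PK in its last block. No footnote restricts it, and the table's abbreviation line confirms what is meant: "PDILI=potential drug-induced liver injury; PK=pharmacokinetic; RNA=ribonucleic acid; ULN=upper limit of normal". Section 4.3.3 gives the analyte: "The PK variable is the plasma concentration of bimekizumab".

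Two sentences say where the results go:
- 12.2.1.3, to the Sponsor: "Results of the laboratory measurements and information collected are to be submitted to the Sponsor on the corresponding eCRF".
- 12.2.1, to the site as well: "The results of all monitoring, including laboratory testing and other testing, should be made available to the study site and Sponsor".

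Section 7.9 sets the blind: "All Sponsor and Investigator site personnel involved in the study will be blinded to the randomized IMP assignment with the following exceptions". Two exceptions follow. One is the unblinded staff who prepare and give the injections. The other is "Bioanalytical staff analyzing blood samples for bimekizumab and anti-bimekizumab antibody determination". The section adds: "Study monitors and study site personnel blinded to treatment assignment will not discuss or have access to any drug-related information".

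For routine PK samples, Section 10.1 puts the collection time and date on the eCRF and refers to a bioanalytical report for the analysis. It also says: "Pharmacokinetic samples from subjects receiving adalimumab will not be analyzed". Those samples are stored.

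**The concern.** The routing sentences in 12.2.1 and 12.2.1.3 cover every result of the work-up, and one of those results reveals treatment. Section 7.9 says the people at the receiving end are blinded. For the PK result, a site or study team that obeys one section disobeys the other.

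At stake is who knows the arm when judgements are made about a liver event. The Investigator records relatedness to IMP (12.1.2.1, 12.1.2.3) and may keep some PDILI subjects on IMP at discretion (6.3.1). The Sponsor's responsible physician is one of the parties who approve a rechallenge (12.2.1.2.1). The Investigator may also score PASI and IGA (Section 9). Liver enzyme changes are a pre-specified safety topic (12.1.1.4). A disclosure by this route would also bypass the code break in 7.9.1.2, which is controlled and has to be documented.

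**Working it through.** The plan states no figure on this point, so there is nothing to reproduce. The check is a reading of the sections against each other, with supporting arithmetic.

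**1. Do the rules conflict?**

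| Question | 12.2.1 and 12.2.1.3 | 7.9 and 10.1 |
|---|---|---|
| Is PK covered? | Yes, listed in Table 12-4 | Yes, bimekizumab assay results |
| Sponsor receives the result? | Yes, on the eCRF | Sponsor personnel are blinded |
| Site receives the result? | Yes (worded as should) | Blinded site staff have no access |
| What goes on the eCRF? | Results | For routine PK, collection time and date |
| Exemption for PK? | None | Not addressed for PDILI samples |

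The documents do not reconcile the two columns. Elsewhere the Protocol does exempt a result when that is intended: footnote k of Table 5-1 keeps HIV results off the eCRF. Table 12-4 has footnotes on the drug screen, prothrombin time and pregnancy test, but none on PK.

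**2. What does a value reveal before Week 24?** Only the two bimekizumab arms receive bimekizumab before the switch (7.2, Table 7-1). Their longest dosing gap in that period is 8 weeks (Week 16 to Week 24, Q4W/Q8W arm). With the half-lives in 2.2.1.1 (27.81 and 28.25 days), the fraction of a dose remaining after t days is 0.5^(t / half-life):
- 28 days: 0.498 to 0.503
- 56 days: 0.248 to 0.253
- 140 days: 0.031 to 0.032

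A measurable level is therefore expected in treated bimekizumab subjects (the assay limit is not given), and a measured level identifies a bimekizumab arm. The period covers the Week 16 co-primary endpoints and all tested secondary endpoints, since Week 24 assessments precede the switch dose.

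**3. What does no value reveal?** A missing result points to adalimumab only if bimekizumab results are being returned during the blinded period and the 10.1 rule covers PDILI samples. If that rule does not cover them, a missing result is uninformative, and only a reported below-limit value would point that way.

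**4. What does a value reveal after Week 24?** Every arm is then assigned bimekizumab, so for subjects still on treatment presence no longer separates the drugs. A rough first-order steady-state comparison, with r = fraction left at 28 days (0.498 to 0.503), gives:
- Q4W to Q8W trough ratio = 1 + 1/r = 2.99 to 3.01
- Q4W to Q8W peak ratio = 1 + r = 1.50
- Q8W peak to Q4W trough = 1 / [r(1 + r)] = 1.32 to 1.34

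A Q8W peak lies above a Q4W trough, so the ranges overlap and one value is at most a hint of regimen.

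**5. How many subjects?** No PDILI rate is given. Assuming 0.5% to 3% have a work-up before Week 24: 450 x 0.005 = 2.25 and 450 x 0.03 = 13.5, or about 2 to 14 subjects.

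**The case against.** The tempting stronger reading is that the Protocol, as written, unblinds the Investigator and Sponsor for every subject who has a liver work-up. The documents do not support that, for these reasons:

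- Section 7.9 is the specific rule on blinding and bars blinded site staff and monitors from drug-related information. Section 12.2.1 says only that results should be made available. Section 7.9 also provides unblinded site personnel and unblinded monitors, who could receive the result. Unblinding follows only if 12.2.1 and 12.2.1.3 are applied literally.
- Section 10.1 can be read as governing these samples. The eCRF would then take only the collection time and date, and nothing would be disclosed. No turnaround time for PK results is given anywhere.
- Section 7.9 defers to a study manual and site blinding plan, and 10.1 to a laboratory manual. None is available here, and release of PK results may be handled there.
- Drug identification stops at the Week 24 switch.

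The consequences are also narrower than a reader might infer. The SAP's hepatic-event table (10.2.3.8) takes events regardless of investigator relatedness, and potential Hy's Law cases are defined by laboratory values (10.3). Rechallenge also needs the DMC and a hepatologist external to the Sponsor. In the 5 to 8xULN category, later withholding and stopping follow liver values. Subjects who stop IMP before Week 16 are nonresponders by imputation (SAP 8.1.2), so scoring cannot change their co-primary outcome.

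All of this stands as a limit on size. It does not remove the conflict: two explicit routing sentences cover PK, and a subordinate manual should not have to override them.

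**Conclusion.** The sections contradict each other for the PDILI PK sample and need to be reconciled. If the routing sentences are followed as written, a bimekizumab concentration returned before Week 24 discloses a bimekizumab arm to people 7.9 keeps blinded, with no code break. The inference from a missing or below-limit result is conditional, as set out in step 3 of the working.

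The size is small: about 2 to 14 subjects, on an assumed rate that has no basis in the documents. The exposure is mainly in investigator relatedness judgements, and so in the SAP's tables by relationship (10.2.2), and in PASI/IGA scoring of the few who continue or restart IMP. The main hepatic-event and Hy's Law summaries do not rest on investigator causality. No sample size, power or error-rate figure changes. A wording correction is warranted because the affected subjects are the ones whose causality judgement most needs the blind.

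**What to change.** In 12.2.1, 12.2.1.3 and Table 12-4:

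- Exempt PK concentrations from eCRF entry and from release to blinded site and Sponsor staff.
- Record only the date and time of collection, as 10.1 does for routine samples.
- Hold the concentration with the bioanalytical laboratory or another unblinded function until study unblinding.
- State whether the 10.1 rule that adalimumab-arm samples are not assayed applies to PDILI samples.

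Sampling does not change. Section 7.9.1.2 already covers cases in which treatment must be known for a subject's care. The cost is a few sentences of Protocol text, with matching laboratory-manual wording. The downside is that the site does not have the concentration in real time.
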